Appendix 4. Tanner Stages*

1. Pubic hair (male and female)	
Tanner I	no pubic hair at all (prepubertal Dominic state)
Tanner II	small amount of long, downy hair with slight pigmentation at the base of the penis and scrotum (males) or on the labia majora (females)
Tanner III	hair becomes more coarse and curly, and begins to extend laterally
Tanner IV	adult-like hair quality, extending across pubis but sparing medial thighs
Tanner V	hair extends to medial surface of the thighs
2. Genitals (male) (One standard deviation around mean age)	
Tanner I	Testes, scrotum, and penis about same size and proportion as in early childhood
Tanner II	Enlargement of scrotum and testes; skin of scrotum reddens and changes in texture; little or no enlargement of penis (10.5-12.5)
Tanner III	Enlargement of penis, first mainly in length; further growth of testes and scrotum (11.5-14)
Tanner IV	Increased size of penis with growth in breadth and development of glans; further enlargement of testes and scrotum and increased darkening of scrotal skin (13.5-15)
Tanner V	Genitalia adult in size and shape
3. Breasts (female)	
Tanner I	no glandular tissue: areola follows the skin contours of the chest
Tanner II	breast bud forms, with small area of surrounding glandular tissue; areola begins to widen
Tanner III	breast begins to become more elevated, and extends beyond the borders of the areola, which continues to widen but remains in contour with surrounding breast
Tanner IV	increased breast size and elevation; areola and papilla form a secondary mound projecting from the contour of the surrounding breast
Tanner V	breast reaches final adult size; areola returns to contour of the surrounding breast, with a projecting central papilla.

* Chart referenced from Marshall WA, Tanner JM, variations in the pattern of pubertal changes in boys and girls {[Marshall 1969](#), [Marshall 1970](#)}

Appendix 5. Pregnancy Precautions, Definition for Female of Childbearing Potential, and Contraceptive Requirements

1) Background

Ribavirin is contraindicated in pregnancy as significant teratogenic and embryocidal effects have been demonstrated in all animal species tested. Pregnancy must be excluded before the start of treatment with study drugs and prevented thereafter by reliable contraceptive methods.

Pregnancy tests will be performed regularly throughout this study. Furthermore, RBV is known to accumulate intracellularly where it is cleared slowly, and is also excreted in semen. Therefore, extreme care must be taken to avoid pregnancy during RBV therapy and for up to 6 months following completion of treatment (7 months for males). Please refer to the latest version of the product insert for additional information.

Non-clinical toxicity studies of LDV/SOF FDC demonstrated no adverse effect on fertility or embryo-fetal development. However, there are no clinical studies of LDV/SOF FDC in pregnant women. Please refer to the latest version of the investigator's brochure for additional information.

2) Definition of Female of Childbearing Potential and Contraceptive Requirements for Female Subjects (and their male partners)

For the purpose of this trial, all post-menarchal females will be considered to be of childbearing potential, unless there is documentation of irreversible ovarian failure or surgical sterilization.

Post-menarchal females must have a negative serum pregnancy test at Screening and a negative urine pregnancy test on the Day 1 visit prior to dosing. They must also agree to one of the following from 3 weeks prior to Day 1 until 6 months after last dose of RBV or 30 days after last dose of LDV/SOF FDC if not taking RBV:

- Complete abstinence from intercourse. Abstinence is acceptable method of contraception only when it is in line with the subject's preferred and usual lifestyle. Periodic abstinence (e.g., calendar, ovulation, symptothermal, post-ovulation methods) and withdrawal are not acceptable methods of contraception.

Or

- Consistent and correct use of 1 of the following methods of birth control listed below, in addition to a male partner who correctly uses a condom, from the date of Screening until 6 months after last dose of RBV or 30 days after the last dose of LDV/SOF FDC if not taking RBV:

— intrauterine device (IUD) with a failure rate of < 1% per year

— female barrier method: cervical cap or diaphragm with spermicidal agent

— tubal sterilization

- vasectomy in male partner
- implants of levonorgestrel
- injectable progesterone
- oral contraceptives (either combined or progesterone only)
- contraceptive vaginal ring
- transdermal contraceptive patch

3) Contraceptive Requirements for Male Subjects (and their female partners)

All male study participants must agree to consistently and correctly use a condom from Day 1 until 7 months after last dose of RBV or 90 days after the last dose of LDV/SOF FDC if not taking RBV. If their female partner is of childbearing potential (as defined above), their female partner must use 1 of the methods of birth control listed above from the date of Screening until 7 months after last dose of RBV or 90 days after last dose of LDV/SOF FDC if not taking RBV.

Male subjects must agree to refrain from sperm donation for at least 7 months after last dose of RBV or 90 days after the last dose of LDV/SOF FDC if not taking RBV.

4) Procedures to be Followed in the Event of Pregnancy

Subjects will be instructed to notify the investigator if they become pregnant at any time during the study, or if they become pregnant within 6 months (7 months for partners of male subjects) of last RBV dose or 30 days (90 days for partners of male subjects) of last LDV/SOF FDC dose if not taking RBV. Subjects who become pregnant or who suspect that they are pregnant must report the information to the investigator and discontinue study drug immediately. Subjects whose partner has become pregnant or suspects she is pregnant must report the information to the investigator.

Instructions for reporting pregnancy, partner pregnancy, and pregnancy outcome are outlined in Section [8.5.2.1](#).

ICH	International Conference on Harmonization (of Technical Requirements for Registration of Pharmaceuticals for Human Use)
LDV	Ledipasvir
LLT	lower level term
LLOQ	lower limit of quantitation
MedDRA	Medical Dictionary for Regulatory Activities
PedsQL™	Pediatric Quality of Life Inventory™
PK	pharmacokinetics
PT	preferred term
Q1	first quartile
Q3	third quartile
RBV	ribavirin
RNA	ribonucleic acid
SAE	serious adverse event
SAP	statistical analysis plan
SI (units)	International system of units
SOC	system organ class
SOF	Sofosbuvir

SVR	sustained virologic response
SVRx	sustained virologic response x weeks after stopping study drug
TEAE	treatment-emergent adverse events
TFLs	tables, figures, and listings
ULN	upper limit of normal
WBC	white blood cell
WHO	World Health Organization

PHARMACOKINETIC ABBREVIATIONS AND DEFINITIONS

λ_z	terminal elimination rate constant, estimated by linear regression of the terminal elimination phase of the log plasma/serum concentration versus time curve of the drug
AUC	area under the plasma/serum concentration versus time curve
AUC _{tau}	area under the plasma/serum concentration versus time curve over the dosing interval
CL	systemic clearance of the drug after intravenous administration
CL/F	apparent oral clearance after administration of the drug: CL/F = Dose/AUC _{inf} , where “Dose” is the dose of the drug
C _{max}	maximum observed plasma/serum concentration of drug
C _{tau}	observed drug concentration at the end of the dosing interval
E _{max}	maximum (pharmacodynamic) effect
t _{1/2}	estimate of the terminal elimination half-life of the drug in serum/plasma, calculated by dividing the natural log of 2 by the terminal elimination rate constant (λ_z)
T _{max}	time (observed time point) of C _{max}

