66-80 (145 – 176)	1000 mg/day	2 × 200-mg capsules A.M. 3 × 200-mg capsules P.M.
81-105 (178-231)	1200 mg/day	3 × 200-mg capsules A.M. 3 × 200-mg capsules P.M.
>105 (>231)	1400 mg/day	3 × 200-mg capsules A.M. 4 × 200-mg capsules P.M.

* Note: Subjects with a body weight greater than or equal to 47 kg may utilize the RBV oral solution if necessary.

The morning dose of RBV will be taken with food and a weight and/or age-appropriate dose of LDV/SOF FDC. The evening dose of RBV will be taken with food.

Reference Therapy: None

Evaluation Criteria:

- Safety: AEs, laboratory tests, physical examinations, and vital sign measurements will be collected throughout the study.
 - Efficacy: Efficacy will be evaluated using scheduled assessments of HCV RNA performed using COBAS[®] AmpliPrep/COBAS[®] TaqMan[®] HCV Test.
 - PK: For subjects in the PK Lead-in, the steady-state PK of LDV, SOF, and its major metabolites (GS-331007 and GS-566500) will be assessed at Day 10. For Cohorts 1 and 2, plasma samples will be collected for PK analyses following dosing of study drug on Day 10 at the following time points: 0 (predose), 0.5, 1, 2, 3, 4, 5, 8, and 12 hours postdose (with predose also serving as t = 24). For Cohort 3, plasma samples for PK analyses will be collected at the following time points: 0 (predose), 0.5, 2, 4, 8, and 12 hours postdose (with predose also serving as t = 24).
-

Plasma PK parameters such as C_{max} , T_{max} , C_{last} , T_{last} , C_{tau} , AUC_{tau} , and $t_{1/2}$ will be estimated.

PPD

For Treatment Group 2 subjects, a PK blood sample will be collected at all visits while on treatment: a PK sample will be collected between 15 minutes to 4 hours post-dose at Weeks 4 and 8 as applicable. A PK sample will be collected at any timepoint at all remaining visits, as applicable. The PK of GS-331007, SOF and LDV will be assessed.

The effect of age and LDV/SOF FDC dose on PK (GS-331007, SOF, and LDV) will be explored.

Statistical Methods:

For the PK Lead-in, plasma PK parameters C_{max} , T_{max} , C_{last} , T_{last} , C_{tau} , AUC_{tau} , AUC_{last} , and $t_{1/2}$ will be estimated. The PK parameters will be summarized by cohort. The effect of age and LDV/SOF FDC dose on PK (GS-331007, SOF, and LDV) will be explored.

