2. OBJECTIVES

The primary objective of the PK Lead-in Phase of this study is:

- To evaluate the steady state pharmacokinetics (PK) and confirm the dose of LDV/SOF FDC in chronic HCV-infected pediatric subjects

The secondary objective of the PK Lead-in Phase of this study is:

- To evaluate the safety, tolerability, and antiviral activity of 10 days of dosing of LDV/SOF FDC in chronic HCV-infected pediatric subjects

The primary objective of the Treatment Phase of this study is:

- To evaluate the safety and tolerability of LDV/SOF FDC +/- RBV for 12 or 24 weeks in chronic HCV-infected pediatric subjects

The secondary objectives of the Treatment Phase of this study are:

- To determine the antiviral efficacy of 12 or 24 weeks of LDV/SOF FDC +/- RBV treatment in chronic HCV-infected subjects (including the impact of HCV genotype, IL28B genotype, and prior treatment experience), as assessed by the proportion of subjects with SVR 12 weeks after completion of treatment (SVR12)
- To determine the antiviral efficacy of 12 or 24 weeks of LDV/SOF FDC +/- RBV treatment in chronic HCV-infected subjects, as assessed by the proportion of subjects with SVR 4 and 24 weeks after completion of treatment (SVR4 and SVR24)
- To evaluate the kinetics of circulating HCV RNA during treatment and after completion of treatment
- To evaluate the emergence of viral resistance to LDV and SOF during treatment and after completion of treatment
- To evaluate acceptability
- assessed by swallowability of tablets and palatability of granules.
- To evaluate the effect of growth and development on pediatric subjects during and after treatment

The exploratory objective of this study is:

- PPD

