 - Urine pregnancy test (females of childbearing potential only). If the urine pregnancy test is positive, the Intensive PK sampling will not be completed. The positive result will be confirmed with a serum pregnancy test.
- Obtain blood samples for the following laboratory analyses:
 - Hematology
 - Chemistry

- Coagulation tests
- HCV RNA
- Viral sequencing (archive)
- Perform intensive PK sampling:
 - Blood samples will be collected at 0 (predose, ≤ 30 minutes prior to dosing). After collection of the predose sample, subjects will be provided a standardized meal. Within 5 minutes after consuming the standardized meal, subjects will be dosed with LDV/SOF FDC per dosing requirements.
 - Post-dose blood samples will be collected as follows:
 - For Cohorts 1 and 2: 0.5, 1, 2, 3, 4, 5, 8, and 12 hours post-dose (with predose also serving as $t = 24$).
 - For Cohort 3 only: 0.5, 2, 4, 8, and 12 hours post-dose (with predose also serving as $t = 24$).
 - Subjects will be restricted from food intake until after collection of the 4-hour post dose blood sample, except for subjects in Cohort 3. Please also refer to the PK manual for details about standardized meals and PK sample processing instructions.

After completing the Day 10 intensive PK visit subjects will then continue to the Week 2 visit in Treatment Phase (described in Section 6.4.2) with no interruption in dosing.

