9.1.2. Primary Endpoints

For the PK Lead-in Phase, the appropriateness of the LDV/SOF FDC dose will be assessed by evaluating the steady-state PK of the LDV/SOF FDC. The primary endpoint for determining steady state PK is AUC_{τ} of GS-331007, SOF, and LDV. Additional steady-state PK parameters of GS-331007, SOF, and LDV (e.g., AUC_{last} , C_{max} , T_{max} , C_{last} , T_{last} , C_{τ} , λ_z , CL/F , V_z/F and $t_{1/2}$) will be estimated and summarized as described in Section 9.4.

For the Treatment Phase, the primary safety endpoint is any AE leading to permanent discontinuation of study drug (s).

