1.2.1. PK Lead-in Phase

The PK Lead-in Phase will evaluate and/or confirm the age appropriate LDV/SOF FDC dose by analyzing PK, safety, and antiviral activity of LDV/SOF FDC through 10 days of dosing.

At least 10 treatment-naïve subjects without history of cirrhosis will be sequentially enrolled into each of the following 3 cohorts:

- Cohort 1: 12 to < 18 years old, weighing ≥ 45 kg
- Cohort 2: 6 to < 12 years old, weighing ≥ 17 kg and < 45kg
- Cohort 3: 3 to < 6 years old
 - At least 4 subjects weighing ≥ 17 kg
 - At least 4 subjects weighing < 17 kg

Intensive PK and safety results through Day 10 of each Cohort will be reviewed to confirm the appropriateness of the LDV/SOF FDC dose for that age group as well as to determine the age-appropriate dose to be evaluated in the PK Lead-in Phase of the next age Cohort.

Subjects enrolled in the PK Lead-in Phase will immediately enroll in the Treatment Phase as they complete Day 10 of PK Lead-in. They will continue dosing with LDV/SOF FDC with no interruption of study drug administration until the appropriateness of the dose is confirmed by PK and safety data from the PK Lead-in Phase.

Cohort 1 subjects received LDV/SOF FDC (90 mg/ 400 mg adult tablet or 4×22.5 mg/100 mg tablets if determined necessary based on LDV/SOF FDC swallowability assessment) for 10 days with intensive PK conducted on Day 10.

Cohort 2 subjects received LDV/SOF FDC 45 mg/ 200 mg (2×22.5 mg/ 100 mg tablets) for 10 days with intensive PK conducted on Day 10.

Cohort 3 subjects weighing ≥ 17 kg received LDV/SOF FDC 45 mg/ 200 mg (4×11.25 mg/ 50 mg packets containing granules) for 10 days with intensive PK conducted on Day 10.

Cohort 3 subjects weighing <17 kg received LDV/SOF FDC 33.75 mg/ 150 mg (3×11.25 mg/ 50 mg packets containing granules) for 10 days with intensive PK conducted on Day 10.

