8. PHARMACOKINETIC ANALYSES

8.1. PK Analysis in the PK Lead-in Phase (Intensive PK Analysis)

Intensive PK Analysis will be performed using the PK Lead-in Phase Intensive PK Analysis Set. Concentrations of SOF, GS-331007 and LDV from subjects in the PK lead-in Phase over sampling time will be listed and summarized using descriptive statistics (n, arithmetic mean, geometric mean and its 95% confidence interval, coefficient of variation [%CV], SD, median, Q1, Q3, minimum, and maximum) by nominal time and cohort. For Cohorts 1 and 2, plasma samples will be collected for PK analyses following dosing of study drugs on Day 10 at the following time points: 0 (predose), 0.5, 1, 2, 3, 4, 5, 8, and 12 hours postdose. For Cohort 3, plasma samples for PK analyses will be collected at the following time points: 0 (predose), 0.5, 2, 4, 8, and 12 hours postdose. PK parameters from subjects in the PK lead-in Phase will be summarized (e.g; AUC_{τ} , AUC_{last} , C_{max} , T_{max} , C_{last} , T_{last} , C_{τ} , $T_{1/2}$, volume of distribution and clearance, as appropriate) by cohort.

To confirm the appropriateness of LDV/SOF FDC dose for each age group, PK parameters for SOF, GS-331007 and LDV will be compared between each age group from this study and the LDV/SOF FDC NDA patient population (which includes population-PK derived PK exposure data from adult Phase 2 and 3 studies) by carrying out an analysis of variance (ANOVA) for log-transformed AUC_{τ} of GS-331007 and LDV as the primary endpoint and C_{max} of GS-331007 and LDV as a secondary endpoint. Geometric Mean Ratio and its 90% confidence interval will be provided.

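### The SAP defines CL/F as Dose/AUCinf, a single-dose formula, but the only Lead-in intensive profile is at steady state, where CL/F is Dose/AUCtau

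*SAP*

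**What the plan says.** The SAP's pharmacokinetic definitions describe CL/F as "apparent oral clearance after administration of the drug: CL/F = Dose/AUC", with the subscript inf. No steady-state form is given. The same list defines AUCtau as "area under the plasma/serum concentration versus time curve over the dosing interval" but does not use it for clearance, and it has no entry for AUCinf.

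The Lead-in is a steady-state evaluation. Its primary objective in Protocol Section 2 is "To evaluate the steady state pharmacokinetics (PK) and confirm the dose of LDV/SOF FDC in chronic HCV-infected pediatric subjects". SAP Section 1.2.1 has each cohort dosed "for 10 days with intensive PK conducted on Day 10", and no intensive profile is planned after the first dose. Sampling stops at 12 h, and the 24 h point is filled in from the trough ("with predose also serving as t = 24", Protocol Synopsis).

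Clearance is a planned output. Protocol Section 9.1.2 lists CL/F and Vz/F under "Additional steady-state PK parameters of GS-331007, SOF, and LDV", and Section 9.4 summarizes them by cohort and overall. SAP Section 8.1 adds "volume of distribution and clearance, as appropriate" to its by-cohort summaries. AUCtau and AUClast are in all three parameter lists; AUCinf is in none.

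**The concern.** At steady state the amount eliminated in one dosing interval equals one bioavailable dose, so CL/F = Dose/AUCtau. Under linear kinetics AUCinf after a single dose has the same value as steady-state AUCtau, which is why the SAP's formula works for a first dose. On Day 10 it does not. The area from the Day 10 dose to infinity includes drug carried over from the nine earlier doses, while the numerator is still one dose, so the ratio is too small.

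This matters most for LDV, whose trough is high relative to its peak: 247/364 = 68% of Cmax in adults (Protocol Table 9-1). Followed literally, the SAP would produce a pediatric LDV clearance that contradicts the AUCtau in the same report. Vz/F would be low by the same factor if computed as CL/F divided by λz.

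**Working it through.** The documents state no CL/F value, LDV half-life or AUCinf/AUCtau ratio, so there is no plan figure to reproduce.

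**Inputs: LDV arithmetic means**

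| Group | Source (Protocol) | LDV dose | AUCtau (ng·h/mL) | Cmax (ng/mL) | Ctau (ng/mL) |
|---|---|---|---|---|---|
| Adults | Table 9-1 | 90 mg | 8530 | 364 | 247 |
| Cohort 1 | Table 1-3 | 90 mg | 10200 | 564 | 319 |
| Cohort 2 | Table 1-4 | 45 mg | 7520 | 432 | 248 |

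**Formula.** AUCinf extrapolated from Day 10 = AUCtau + Ctau/λz, with λz = ln 2 / half-life. The factor by which CL/F is too low is

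AUCinf/AUCtau = 1 + (Ctau/AUCtau) × half-life / ln 2.

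These are ratios of arithmetic means, so the results are approximate.

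**Step 1. Half-life as an assumption, 20 to 50 h**

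| Group | 20 h | 30 h | 40 h | 50 h |
|---|---|---|---|---|
| Adults | 1.84 | 2.25 | 2.67 | 3.09 |
| Cohort 1 | 1.90 | 2.35 | 2.80 | 3.26 |
| Cohort 2 | 1.95 | 2.43 | 2.90 | 3.38 |

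Example, Cohort 1 at 30 h: λz = 0.693/30 = 0.0231 per h; Ctau/λz = 319/0.0231 ≈ 13,800; AUCinf ≈ 10,200 + 13,800 = 24,000; ratio 2.35.

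The overall range is 1.84 to 3.38, so CL/F would be 46% to 70% too low (1 − 1/1.84 and 1 − 1/3.38).

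**Step 2. Apparent half-life from the tables' own decline.** Take λ = ln(Cmax/Ctau)/(24 − Tmax). Tmax is not tabulated, so it is assumed to lie between 4 and 12 h, the last drawn sample. Each cell shows apparent half-life, then factor.

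| Group | Tmax 4 h | Tmax 8 h | Tmax 12 h |
|---|---|---|---|
| Adults | 35.8 h, 2.49 | 28.6 h, 2.19 | 21.5 h, 1.90 |
| Cohort 1 | 24.3 h, 2.10 | 19.5 h, 1.88 | 14.6 h, 1.66 |
| Cohort 2 | 25.0 h, 2.19 | 20.0 h, 1.95 | 15.0 h, 1.71 |

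The two pediatric cohorts give 1.66 to 2.19, or CL/F about 40% to 54% too low. This decline may mix distribution with elimination. It may therefore understate the terminal half-life, and it does not exclude the upper part of the Step 1 range.

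**Step 3. Clearance under each definition.** Dose/AUCtau gives 90,000 µg / 10,200 µg·h/L = 8.8 L/h in Cohort 1, 45,000/7,520 = 6.0 L/h in Cohort 2 and 90,000/8,530 = 10.6 L/h in adults. In Cohort 1, Dose/AUCinf extrapolated from Day 10 gives 4.6 L/h at 20 h, 3.8 L/h at 30 h and 2.7 L/h at 50 h.

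**The case against.** The strongest reply is that this is an entry in a generic definitions list, which also covers intravenous clearance and Emax, neither of which this study plans to report. AUCinf is not a listed Lead-in parameter, and SAP Section 8.1 qualifies its clearance summary, so an analyst may well divide by AUCtau. That stands. It means the bias follows only from literal use and cannot be stated as what the study will report. It does not rescue the definition, which is the SAP's only formula for a quantity the protocol calls a steady-state parameter, and whose denominator the plan does not otherwise produce.

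Three stronger readings are tempting, and the documents do not support them.

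- A reader might infer a fixed error of about 2.3 to 3.1. With adult means that needs a half-life of about 31 to 50 h, which the documents do not give. The long end can be suggested only by the few subjects in Study GS-US-337-2091 dropped for pre-dose LDV above 5% of Cmax after a 9-day washout: 5% remaining at 216 h implies 50 h. The analyzed LDV numbers were 42, 39 and 40 of 42 across the treatments, so those were 0, 3 and 2 subjects. The pediatric tables point mostly lower.
- A reader might infer that dose selection for a later cohort is compromised. Protocol Section 1.5 scales adult exposures by correlations of body weight with liver size and renal capacity, plus the granule bioavailability data. It does not say that it uses Lead-in CL/F. Cohort 3 is the last cohort, and SAP Section 1.2.1 already describes its dosing in the past tense.
- Because the last drawn sample is at 12 h and the 24 h value is copied from the trough, a reader might infer that noncompartmental LDV half-life, λz and Vz/F should be withheld. These values will be imprecise, but withholding them is a preference that would remove parameters the protocol lists. SAP Section 8.2 already plans a population model on pooled intensive and sparse samples.

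**Conclusion.** The definition is wrong as written, and the consequence is minor. Applied literally to an AUCinf extrapolated from Day 10, it would make LDV CL/F too low by a factor of about 1.8 to 3.4 for assumed half-lives of 20 to 50 h. The pediatric tables' own decline gives about 1.7 to 2.2. Both ranges rest on arithmetic means, and the second also on Tmax between 4 and 12 h. The error for SOF and GS-331007 was not sized.

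No decision depends on it. The comparison with adults and the dose confirmation use AUCtau (Protocol Sections 9.1.2 and 9.4, SAP Section 8.1). So does the check on individual exposures against adult percentiles. The population PK analysis is separate. What is at risk is a descriptive clearance, and possibly a volume, that disagrees with the AUCtau reported beside it.

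**What to change.** In the SAP's pharmacokinetic definitions, replace the CL/F formula with CL/F (CLss/F) = Dose/AUCtau for the Day 10 steady-state profiles. Add one sentence to SAP Section 8.1 saying that clearance is computed this way and that Vz/F is derived from that value and λz. Reusing the predose sample at 24 h already assumes steady state and already yields AUCtau, so the denominator is available. The cost is one changed line and one added sentence, with no new data, sampling or protocol amendment.
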